4.4 ANTI-DRUG ANTIBODIES

4.4.1 Available data

Presence of anti-drug antibodies (ADA) to efgartigimod is measured at visits 1, 4, 8, 13, 19, 23, End-of-Treatment visit and follow-up visit 2.

ADA samples are analyzed in a 3-tiered approach:

- All samples are evaluated in the ADA screening assay and are scored ADA screening positive or negative
- If a sample scored positive in the ADA screening assay, it is further evaluated in the confirmatory assay and is scored confirmed positive (positive immunodepletion) or confirmed negative (negative immunodepletion)
- If a sample is scored as confirmed positive, the samples are further characterized in the ADA titration assay (to determine titer) and are also further analyzed in the NAb assay to confirm neutralizing activity (positive or negative)

If available, a titer result will be reported for the ADA confirmed positive samples. However, a titer result is not always available:

- In case the ADA confirmed positive sample could not be run in the titration assay (e.g. due to insufficient sample volume/quality to perform the titer analysis), the result will be described as 'positive immuno-depletion' and the sample should be considered as ADA positive.
- If a sample is negative in the titration assay, it will be reported as 'negative titer' but it should be considered as ADA positive since it was confirmed positive in the second tier.
- If a sample could not be analyzed or reported as 'positive screen', the ADA sample status is ADA unevaluable.

An overview of this 3-tiered approach and all possible ADA sample results that will be reported by the laboratory is given below. From these reported ADA sample results a final ADA sample status needs to be derived during the statistical analysis, as presented in the final column ('Final ADA Outcome'):

Figure 1: ADA sample status

4.4.2 Derivation rules

4.4.2.1 PATIENT CLASSIFICATION FOR ADA

Table 9 below gives an overview of how the ADA patient classification will be derived, starting from the patient baseline ADA sample status. See also section 4.4.1:

SGS Statistical Analysis Plan		
ARGX-113-1801	Final analysis	Final 1.0 of 28MAR2022

Table 9: Patient classification for ADA

Patient ADA	Highest ^c post baseline sample status				
classification	ADA negative	ADA positive (missing titer ^a)	ADA positive (negative) titer ^b or positive titer)		ADA not evaluable
Baseline ADA sample status					
ADA negative	ADA negative	Treatment Induced ADA	Treatment In	duced ADA	ADA unevaluable
ADA positive (missing titer ^a)	Treatment Unaffected ADA	ADA unevaluable	ADA une	valuable	ADA unevaluable
ADA positive (negative titer ^b or positive titer)	Treatment Unaffected ADA	ADA unevaluable	titer < 4 x baseline titer: Treatment Unaffected ADA	titer ≥ 4x baseline titer: Treatment Boosted ADA	ADA unevaluable
ADA not evaluable	ADA unevaluable	ADA unevaluable	ADA une	valuable	ADA unevaluable

^a Samples with missing titer have as reported ADA result 'positive immunodepletion';

^b Results reported as 'negative titer', i.e. titer value <1 will be set to value of 1;

^c Highest sample status, with order: (from low to high): ADA unevaluable, ADA negative, ADA positive (missing titer /positive immunodepletion), ADA positive with titer < 1 ('negative titer' as reported ADA result, titer value set to 1), ADA positive with titer ≥ 1 (i.e. positive titer and selecting the sample with highest titer)

ADA evaluable patient = patient classified as any of following categories: ADA negative, treatment unaffected ADA, treatment induced ADA, treatment boosted ADA.

ADA unevaluable patient = patient classified as ADA unevaluable or with missing baseline ADA sample or without post-baseline ADA samples

Note: Fourfold difference in titer values is considered significant in case a twofold serial dilution is applied (= two times the dilution factor) (reference to Shankar et al., 2014)⁹.

ADA incidence = percentage of patients with treatment-induced or treatment-boosted ADAs (denominator: number of evaluable patients).

ADA prevalence = percentage of patients with treatment-unaffected ADA, treatmentinduced ADA or treatment-boosted ADA (denominator: number of evaluable patients).

4.4.2.2 PATIENT CLASSIFICATION FOR NAB

All ADA confirmed positive samples will also be evaluated in the NAb assay. All samples that were not analyzed in the NAb assay (i.e. the ADA negatives) are per default NAb negative. Also, if a NAb sample is not reported, the NAb sample status is NAb unevaluable.

All samples evaluated in the NAb assay will be scored as NAb positive, NAb negative or NAb unevaluable by the laboratory. Based on these results, the patients

SGS	SGS Statistical Analysis Plan	
ARGX-113-1801	Final analysis	Final 1.0 of 28MAR2022

will be categorized based on their baseline and post-baseline sample status as detailed in Table 10.

Table 10:	Patient	classification	for NAb
-----------	---------	----------------	---------

Patient NAb classification	Highest ^a post baseline NAb sample status			
	NAb negative	NAb positive	NAb not evaluable	
Baseline NAb sample status				
NAb negative			NAb unevaluable	
NAb positive	baseline neg – post- baseline neg baseline pos – post- baseline neg	baseline neg – post- baseline pos baseline pos – post- baseline pos	NAb unevaluable	
NAb not evaluable	NAb unevaluable	NAb unevaluable	NAb unevaluable	

a: Highest sample status in order: (from low to high): NAb unevaluable, NAb negative, NAb positive.

Note: At least 1 sample (which is not unevaluable) should be present.

NAb unevaluable patient = patient classified as NAb unevaluable or with missing baseline NAb sample or without post-baseline NAb samples

NAb incidence = percentage of patients with patient classification 'baseline neg – post-baseline pos' and 'baseline pos – post-baseline pos' (denominator: number of evaluable patients).

NAb prevalence = percentage of patients with patient classification 'baseline neg – post-baseline pos', 'baseline pos – post-baseline pos' or 'baseline pos – post-baseline neg'. (denominator: number of evaluable patients).

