^c For further confirmation of eligibility at visit 1, the assessment of inclusion and exclusion criteria should be performed prior the start of any trial-related procedure and randomization.

^d Platelet count is measured locally. Post-baseline platelet count can be performed within 1 day of the next procedure as per the SoA (both dosing and non-dosing visits). Eligible patients should have a mean platelet count of <30×10⁹/L from 2 counts: 1 platelet count during the screening period and the predose platelet count on the day of randomization (visit 1).

In addition, the absolute immature platelet count (IPF#) and the fraction of immature platelets related to mature platelets (IPF%) will be measured locally in facilities equipped with a hematology analyzer which can determine this platelet subset.

^e Patient-reported outcomes and QoL assessments need to be performed preferably after the platelet count assessment.

f Height will only be measured at the screening visit.

g Electrocardiogram will be assessed after the end of the IMP infusion, if any. If no IMP is administered, the ECG will be assessed preferably after the blood sample for platelet counts has been taken.

^h Laboratory assessments include all parameters mentioned in Appendix 1 of the protocol.

i At the screening visit, if the investigator detects 1 or more screening laboratory abnormalities, the result(s) should be confirmed if still within the screening window. For rescreening criteria see Section 4.7.

¹ Only for women of childbearing potential. To be done at least every 4 weeks.

k At the screening visit, the total IgG level must be determined by the central laboratory (exclusion criterion 10).

¹ In order to maintain the blind, the IgG testing cannot be performed locally.

^m If the visit does not coincide with an IMP infusion, then the assessment should be performed at the next IMP visit.

ⁿ In samples having a positive ADA titer, samples will be tested for neutralizing ADAs.

^p Both pre- and post-dose to be collected (within 2 hours prior to the start of the IMP infusion and within 30 minutes after the end of IMP infusion, respectively).

^q Randomization to be completed before administration of IMP.

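### SAP Table 10 can class a patient as post-baseline NAb negative when a confirmed ADA-positive sample has no valid NAb result, because an untested ADA-negative sample outranks it

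*SAP*

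**What the plan says.** SAP 4.4.1 describes a tiered assay: screening, then confirmation, then titration and NAb testing of confirmed positives. SAP 4.4.2.2 turns the sample results into a patient class by four rules.

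- ADA-negative samples are not tested for NAb: "All samples that were not analyzed in the NAb assay (i.e. the ADA negatives) are per default NAb negative".
- A missing NAb result has its own status: "Also, if a NAb sample is not reported, the NAb sample status is NAb unevaluable". The laboratory may also return NAb unevaluable for a sample that it did run.
- The patient takes the highest post-baseline status: "Highest sample status in order: (from low to high): NAb unevaluable, NAb negative, NAb positive".
- The minimum data for classification is one usable sample: "At least 1 sample (which is not unevaluable) should be present".

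NAb incidence is the percentage of evaluable patients in the two post-baseline-positive classes. The NAb class also defines the columns of the tables of drug concentration, platelet change, total IgG, sustained response, TEAEs, serious TEAEs and hypersensitivity events (SAP 4.2.3, 4.4.3 and 5.1.3).

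Footnote n of the schedule in SAP 9.4.1, repeated in the protocol schedules, describes NAb testing differently: "In samples having a positive ADA titer, samples will be tested for neutralizing ADAs".

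**The concern.** Since ADA-negative samples are NAb negative by default, an unresolved NAb status arises mainly in ADA-positive samples, which are the only ones that could be neutralizing. Under footnote a, any ADA-negative sample overrides them. A patient can thus be reported as an evaluable NAb negative when no post-baseline sample of theirs has a valid NAb result.

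Table 10 treats the same gap differently at baseline: an unevaluable baseline sample makes the patient NAb unevaluable whatever follows. The two patient classifications also diverge. With an ADA-negative baseline, such a patient is treatment-induced ADA in Table 9 and NAb negative in Table 10, so appears among the NAb negatives when the two are cross-tabulated.

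What is at stake is descriptive: NAb incidence, and the purity of the NAb-negative comparison group.

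**Working it through.** The plan states no figure to reproduce, so the check applies the rule and then bounds its effect.

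**1. One patient.** SAP 4.4.1 schedules ADA samples at visits 1, 4, 8, 13, 19, 23, End-of-Treatment and follow-up visit 2. That is up to 7 post-baseline samples, or 6 without follow-up visit 2. Take an ADA-negative baseline, a confirmed-positive sample at visit 13 with no valid NAb result, and ADA-negative samples otherwise.

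- Sample statuses: one NAb unevaluable, the rest NAb negative by default.
- Highest status under footnote a: NAb negative.
- Patient class: baseline negative, post-baseline negative, evaluable.

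The result is the same with 2, 6 or 7 post-baseline samples. The patient becomes NAb unevaluable only if the unresolved sample is the sole post-baseline one.

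**2. How often the unevaluable column of Table 10 can apply.** With a NAb-negative baseline and no NAb-positive sample, count the patterns of negative and unevaluable samples that contain at least one unevaluable sample.

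- 6 samples: 2^6 − 1 = 63 patterns; 62 are classed NAb negative.
- 7 samples: 2^7 − 1 = 127 patterns; 126 are classed NAb negative.

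The single exception each time is the pattern with every sample unevaluable. These are counts of patterns, not probabilities.

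**3. Effect on incidence.** Let n be the patients that the SAP counts as evaluable, x those classed post-baseline NAb positive, u the unresolved patients classed negative, and k the number of those u who are truly positive (0 ≤ k ≤ u).

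- As planned: x/n
- Unresolved patients excluded: x/(n − u)
- True value: (x + k)/n, at most (x + u)/n

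The error from the rule is x/n − (x + k)/n = −k/n, which is never positive.

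Full planned enrolment of 117 + 39 = 156, randomized 2:1, gives n = 156 × 2/3 = 104 on efgartigimod. With chronic patients only, n = 117 × 2/3 = 78. All are taken as evaluable. The values of x and u are assumptions, because the documents give neither.

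| n | x | u | As planned | Excluded | Upper bound |
|---|---|---|---|---|---|
| 104 | 0 | 2 | 0.00% | 0.00% | 1.92% |
| 104 | 1 | 1 | 0.96% | 0.97% | 1.92% |
| 104 | 2 | 2 | 1.92% | 1.96% | 3.85% |
| 104 | 4 | 4 | 3.85% | 4.00% | 7.69% |
| 78 | 2 | 2 | 2.56% | 2.63% | 5.13% |
| 78 | 4 | 4 | 5.13% | 5.41% | 10.26% |

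Exclusion moves incidence by at most 0.28 percentage points here (5.41 − 5.13). The upper bound is an extreme, since it takes every unresolved patient as truly positive.

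**The case against.** The best defence is that the situation may hardly arise. SAP 4.4.1 and 4.4.2.2 and protocol 7.6 all send every confirmed positive to the NAb assay, and no document gives a rate of failed or missing results. The unevaluable counts are visible anyway: sample status is tabulated by visit for ADA and again for NAb (SAP 4.4.3), and results are listed by patient (Listing 16.2.6.7). The analyses are descriptive and outside the alpha-controlled hierarchy. Excluding patients is not neutral either: if their unresolved samples were all non-neutralizing, x/(n − u) overstates incidence.

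Most of this stands and limits the size of the point. It does not rescue the rule. The SAP provides for NAb-unevaluable laboratory results, so it foresees the case, and visit-level tables do not correct a patient-level class.

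Three stronger readings are tempting and not supported.

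- *NAb incidence is understated.* That requires an unresolved sample, in a patient with no NAb-positive sample, that was truly neutralizing. The documents establish the direction only.
- *Table 9 has the same defect.* Its order also starts low: "Highest sample status, with order: (from low to high): ADA unevaluable, ADA negative". But a screen-positive sample without confirmation is not a confirmed positive, since the second tier can score it negative. A confirmed positive with a missing titer already ranks above negative, so Table 9 keeps it.
- *Footnote n leaves negative-titer samples untested.* It does not say that only positive-titer samples are tested, and protocol 7.6 and SAP 4.4.1 send all confirmed positives. It is a wording mismatch.

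**Conclusion.** The point holds for Table 10 and is conditional. A patient who has a confirmed ADA-positive post-baseline sample without a valid NAb result, no NAb-positive sample and at least one ADA-negative post-baseline sample is classed post-baseline NAb negative and counted as evaluable. If such patients occur, the rule can bias NAb incidence only downward, and it places patients of unknown status in the NAb-negative group.

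The number affected is not documented. Under the assumed counts, excluding them changes overall incidence by a few tenths of a percentage point at most; the wider gap to the upper bound shows what could be missed.

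A reader might also infer a marked shift in the share of NAb positives within an ADA category (Table 14.2.10.5). The SAP does not support a figure for that. It defines the evaluable denominator for incidence and prevalence, but does not state that this table uses it.

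No hypothesis test and no primary or key secondary result is affected.

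**What to change.** - In Table 10, footnote a, rank a post-baseline sample that is ADA confirmed positive without a valid NAb result above NAb negative and below NAb positive. The patient is then NAb unevaluable unless another post-baseline sample is NAb positive.
- Amend the note on minimum data, so that a default negative no longer suffices when a confirmed positive is unresolved.
- Report the number of such patients, so that a reader can form the bound (x + u)/n.
- Reconcile schedule footnote n with protocol 7.6 and SAP 4.4.1, so that all describe NAb testing of confirmed positives.
- Leave the Table 9 order as it is.

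The cost is a wording change and a few lines of derivation code. A few patients would leave the evaluable denominator. A baseline-NAb-positive patient moved to unevaluable would also leave the prevalence numerator, so the SAP should say whether that is intended.

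### NAb incidence in SAP 4.4.2.2 counts every patient positive at both baseline and post-baseline, with no boost criterion, so it is an upper bound on treatment-related NAb and follows a different rule from ADA incidence

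*SAP*

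**What the plan says.** SAP 4.4.2.2 gives the rule "NAb incidence = percentage of patients with patient classification" and names two classes, negative at baseline then positive, and positive at both times, over evaluable patients. Prevalence ("NAb prevalence = percentage of patients with patient classification") uses the same two classes and adds patients who were positive at baseline and negative afterwards. The NAb result has no titer: "All samples evaluated in the NAb assay will be scored as NAb positive, NAb negative or NAb unevaluable by the laboratory". Samples that are not ADA confirmed positive are not run in the NAb assay and are taken as NAb negative.

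SAP 4.4.2.1 uses another rule for binding antibodies: "ADA incidence = percentage of patients with treatment-induced or treatment-boosted ADAs". Under Table 9, a patient with a baseline titer counts as boosted only at 4 times that titer or more, and below that is treatment-unaffected. The note to the table gives the reason: "Fourfold difference in titer values is considered significant in case a twofold serial dilution is applied". Treatment-unaffected patients enter prevalence only ("ADA prevalence = percentage of patients with treatment-unaffected ADA", together with the induced and boosted classes).

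SAP 4.4.3 repeats the ADA prevalence and incidence tabulations for NAb. SAP 8.1 lists them as parallel tables, 14.2.10.2 for ADA and 14.2.10.4 for NAb, both on the safety analysis set.

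**The concern.** The word incidence has two meanings in adjacent tables. A patient with stable, pre-existing, neutralizing antibody is treatment-unaffected in the ADA table and incident in the NAb table. The SAP neither explains the difference nor lists it in section 6.1.

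A reader of table 14.2.10.4 would take the NAb figure as neutralizing antibody that appeared or rose on study drug, because that is what the ADA figure means. Some or all of it could be reactivity present before the first dose. Assessing immunogenicity is a secondary objective (Protocol 2.2), so the label should say what is counted.

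**Working it through.** The plan states no NAb or ADA rate, so there is no figure to reproduce. The check is algebraic, followed by an illustration with assumed counts.

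**Notation** (evaluable patients, classes from SAP 4.4.2.2):
- a = negative at baseline, positive post-baseline
- b = positive at both times
- c = positive at baseline, negative post-baseline
- E = evaluable patients

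Treatment-related below means arising or boosted after the first dose. It is not a causal judgement.

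**Step 1. What the SAP formula measures.** Incidence = (a + b)/E and prevalence = (a + b + c)/E. They differ by c/E only, the patients who lose positivity. Because a + b is everyone positive post-baseline, incidence here equals any post-baseline positivity.

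**Step 2. What the ADA logic would measure.** Split b into b1 (boosted) and b2 (unaffected). A rule parallel to the ADA one gives (a + b1)/E. The SAP figure exceeds this by b2/E, with 0 ≤ b2 ≤ b. With no NAb titer, the NAb result alone cannot separate b1 from b2. So:
- upper bound on treatment-related NAb: (a + b)/E, the SAP figure
- lower bound: a/E
- maximum overstatement: b/E

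**Step 3. Illustration.** Planned enrolment is 117 + up to 39 = 156 at 2:1 (SAP 1.4), so 156 × 2/3 = 104 on efgartigimod. Assume all are evaluable and a = 2. The values of b are assumptions, not trial data.

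| b | SAP incidence (a + b)/104 | Lower bound a/104 | Maximum overstatement b/104 |
|---|---|---|---|
| 0 | 1.9% | 1.9% | 0.0 points |
| 1 | 2.9% | 1.9% | 1.0 points |
| 2 | 3.8% | 1.9% | 1.9 points |
| 5 | 6.7% | 1.9% | 4.8 points |
| 10 | 11.5% | 1.9% | 9.6 points |

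If b = 5 and one of the five were boosted, the parallel rule would give (2 + 1)/104 = 2.9% and the overstatement would be 4/104 = 3.8 points, below the maximum.

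**Step 4. Coherence with ADA incidence.** NAb-positive samples are a subset of ADA-positive samples. Suppose 2 patients have treatment-induced ADA, 5 are treatment-unaffected and none is boosted, and all 7 are neutralizing whenever ADA positive and stay positive post-baseline. ADA incidence is 2/104 = 1.9% and NAb incidence is (2 + 5)/104 = 6.7%. The subset then has the higher incidence, solely because the two rules treat the same five patients differently.

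**The case against.** The best defence is that a result scored only positive, negative or unevaluable allows no boost rule, so some convention is needed for patients positive at both times. This stands in part, and it rules out several stronger readings.

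- A reader might infer that the figure overstates treatment-related NAb by exactly the share positive at both times. It does not follow: some of those patients may be boosted, so that share is the maximum.
- A reader might infer that a patient positive before dosing can never be incident. That is not the SAP's own ADA rule, which admits baseline-positive patients who are boosted.
- A reader might infer that counting converters alone would make the NAb and ADA figures comparable. It would not, because it drops boosted patients whom ADA incidence keeps. The denominators can differ too: Table 9 makes a patient with a missing baseline titer and a positive post-baseline sample ADA unevaluable, while NAb evaluability does not depend on titer.
- A reader might infer that a listed endpoint is affected. The endpoint in Protocol 3.2 and SAP 1.2.2 is ADA incidence, whose definition is not in question.

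The defence can also say that the information is available. SAP 4.4.3 tabulates patients by NAb class and NAb-positive patients within each ADA class (table 14.2.10.5), listing 16.2.6.7 gives individual results, and tables are shown per treatment, so placebo shows background reactivity. This limits the harm. It does not correct the summary line labelled incidence. SAP 4.4.3 also does not say that table 14.2.10.5 separates converters from patients positive at both times.

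**Conclusion.** The point holds in bounded form. As written, NAb incidence is post-baseline NAb positivity: an upper bound on treatment-related NAb that may overstate it by between zero and b/E. It is not governed by the ADA rule used beside it and can exceed ADA incidence.

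The overstatement is zero if no patient is positive at both times or if all such patients are boosted. Its actual size cannot be known from the documents, and the percentages above rest on assumed counts and full evaluability at 104 patients. The consequence is limited to a descriptive immunogenicity summary. No hypothesis test, alpha-controlled endpoint or efficacy conclusion depends on it. It is minor, but worth correcting because the label misdescribes the quantity.

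**What to change.** Preferred: define NAb incidence in SAP 4.4.2.2 as patients negative at baseline and positive post-baseline, plus only those positive at both times whose ADA class under 4.4.2.1 is treatment-boosted. Report the remaining patients positive at both times in prevalence and in the classification table, and show separately any whose ADA class is unevaluable. State that the ADA titer stands in for a NAb titer, since a fourfold rise in binding antibody does not prove a rise in neutralizing activity.

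Alternative: keep the calculation, relabel it as post-baseline NAb positivity, and report converters separately as newly positive NAb, described as a lower bound.

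Even under the preferred rule, a patient with non-neutralizing ADA at baseline who later becomes NAb positive without a fourfold titer rise would count for NAb and not for ADA. That is a genuine conversion, and a footnote is enough.

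The cost is one definition line or one label with a footnote, plus a small change to table 14.2.10.4. The classifications are already derived, and no new samples or assays are needed.
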